5.1. Power analysis

In none of the studies on ESWT for non-specific low back pain performed so far (Nedelka et al., 2014; Lee et al., 2014; Han et al., 2014; Moon et al., 2016) a definition of treatment success was defined, a Power analysis was reported and the PSEQ score was used to assess clinical outcome. Accordingly, these studies are only of very limited use for the purpose of performing a Power analysis of the proposed study.

Based on anecdotal evidence from several therapists in Europe and Latin America who have been using rESWT for non-specific low back pain for more than a decade we hypothesize that treatment of chronic non-specific low back pain with rESWT alone as described above will result in a success rate of approximately 70%, and the combination of rESWT and C-E drugs in a success rate of approximately 85%. Furthermore, based on our own experience we hypothesize that treatment of chronic non-specific low back pain with C-E drugs alone as described above will result in a success rate of only approximately 35%

On this basis we performed a Power analysis, both for a percentage of 35% as well as for various other percentages (ranging between 10% and 99.9%) of patients with treatment success when treated with C-E drugs alone, accounting for a two sided-confidence interval of 95% (and, thus, a type-1 error rate of 5%). Calculations were performed using the software Open Source Epidemiologic Statistics for Public Health (www.openepi.com). The results are summarized in Tables 7 and 8.

Table 7. Power for the proposed RCT on rESWT plus C-E drugs or rESWT alone for chronic non-specific low back pain, accounting for a two sided-confidence interval of 95% and a percentage of patients with treatment success of 40% when treated with C-E drugs alone (assuming n=50 patients per group).

Percent of patients treated with rESWT plus C-E drugs or C-E drugs alone with treatment success [%]	Power based on Normal approximation [%]	Power based on Normal approximation with continuity correction [%]
99.9	100	100
90	100	100
85	100	100
80	99.8	99.6
70	95.0	92.4
60	71.3	63.5
50	32.7	25.2
40	7.2	3.5
35	1.1	0

Table 8. Power for the proposed RCT on rESWT plus C-E drugs for chronic non-specific low back pain, accounting for a two sided-confidence interval of 95% and a percentage of patients with treatment success of 70% when treated with rESWT alone (assuming n=50 patients per group).

Percent of patients treated with rESWT plus C-E drugs or C-E drugs alone with treatment success [%]	Power based on Normal approximation [%]	Power based on Normal approximation with continuity correction [%]
99.9	99.3	98.3
90	71.2	61.2
85	43.4	33.4
80	20.9	14.2
70	1.1	0

Furthermore, we calculated the minimum sample size in both groups (rESWT, control) that would be necessary for detecting a difference in treatment success between

- the patients treated with rESWT plus C-E drugs and the patients treated with C-E drugs alone,
- the patients treated with rESWT alone and the patients treated with C-E drugs alone, and

- the patients treated with rESWT plus C-E drugs and the patients treated with C-E drugs alone,

accounting for a two sided-confidence interval of 95% and a power of 0.8. Calculations were also performed using the software Open Source Epidemiologic Statistics for Public Health (www.openepi.com). The results are summarized in Tables 9 and 10.

Table 9. Sample size in the proposed RCT on rESWT plus C-E drugs or rESWT alone for chronic non-specific low back pain, accounting for a two sided-confidence interval of 95% and a power of 0.8. The percentage of patients with treatment success when treated with C-E drugs alone was set at 40%.

Sample size of both groups (rESWT, placebo) according to...				
Percent of patients with treatment success when treated with rESWT plus C-E drugs or rESWT alone [%]	Kelsey et al. (1996)	Fleiss et al. (2003)	Fleiss et al. (2003) with continuity correction	
99.9	10	8	11	
90	15	14	17	
85	19	17	22	
80	24	23	28	
70	44	42	49	
60	99	97	107	
50	389	388	408	
45	1502	1501	1540	

Table 10. Sample size in the proposed RCT on rESWT plus C-E drugs for chronic non-specific low back pain, accounting for a two sided-confidence interval of 95% and a power of 0.8. The percentage of patients with treatment success when treated with rESWT alone was set at 70%.

Sample size of both groups (rESWT, placebo) according to...				
Percent of patients with treatment success when treated with rESWT plus C-E drugs or rESWT alone [%]	Kelsey et al. (1996)	Fleiss et al. (2003)	Fleiss et al. (2003) with continuity correction	
99.9	23	22	28	
90	63	62	72	
85	122	121	134	
80	297	296	316	
75	1221	1220	1259	

In summary, the proposed study has a power of more than 0.8 in finding a difference in treatment success (individual improvement of the PSEG score by more than 20 points at 12 weeks after baseline) between rESWT plus C-E drugs and C-E drugs alone, as well as between rESWT alone and C-E drugs alone, for treating chronic non-specific low back pain when randomizing at least 49 patients into each group.

On the other hand, the proposed study does not have a power of more than 0.8 in finding a difference in treatment success (individual improvement of the PSEG score by more than 20 points at 12 weeks after baseline) between rESWT plus C-E drugs and rESWT alone, for treating chronic non-specific low back pain when randomizing less than 134 patients into each group.

In summary, the proposed study can test the following hypotheses in the treatment of chronic non-specific low back pain: (i) rESWT plus C-E drugs is superior to C-E drugs alone, and (ii) rESWT alone is superior to C-E drugs alone. Furthermore, the proposed study can retrieve important pilot data for designing a follow-up study testing the hypothesis that rESWT plus C-E drugs is superior to rESWT alone in the treatment of chronic non-specific low back pain.

Collectively, the results of the Power analysis reinforce the validity of the proposed study protocol for testing efficacy and safety of rESWT using the Swiss DolorClast for chronic non-specific low back pain.

6. Patient protection procedures

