4.12. Blinding of therapists and assessors

- Therapists applying the treatments will not be blinded. This will be done because even when using coded “active” and “placebo” handpieces in a study on ESWT, blinding of ESWT therapists can only be achieved when another person prepares the device before rESWT or sham treatment. This, however, is almost impracticable and has not been done in any of the more than 100 studies on rESWT and fESWT listed in the PEDro database (Schmitz et al., 2015). The solution to this issue is a strict, standardized way of interaction between the ESWT therapist and the patients, irrespective of treatment allocation (as mentioned in a study by Buchbinder et al., 2002). This approach will also be applied in the proposed study.
- All assessments before the first treatment (baseline) and during the follow-up period will be performed by assessors blind to the intervention.

5. Follow-up and statistical analysis

- Follow-up will be the same for all study patients.
- The design of the proposed study guarantees that there will be full compliance with the allocated treatment and, thus, no contamination of one group.
- The patient's age, gender, body mass index, job occupation and duration of non-specific low back pain are potential confounding factors when treating chronic non-specific low back pain with rESWT. Normal distribution of these data will be tested using the D'Agostino-Pearson omnibus test. In case of passing the normality test we will report mean and standard error of the mean of these variables; otherwise we will report inter-quartile ranges of these variables. Comparison between groups will be performed with ANOVA followed by Bonferroni post tests for pairwise comparisons in case of passing the normality test, or the nonparametric Kruskal-Wallis test followed by Dunns tests for pairwise comparisons in case of not passing the initial normality test.
- As outlined in Section "Primary clinical outcome and definition of treatment success" above, the primary clinical outcome will be the PSEQ score at 12 weeks after baseline. Treatment success (i.e., number of patients with individual improvement of PSEQ score by more than 20% at 12 weeks after baseline) will be tested with Fisher's exact test.

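### Table 7 is captioned at 40% success on C-E drugs, but its powers were computed at the hypothesised 35%; Table 9 does use 40%, without a stated reason

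*Combined protocol and SAP*

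**What the plan says.** All of this stands in Section 5.1, Power analysis, unless noted.

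- The assumed control rate: "treatment of chronic non-specific low back pain with C-E drugs alone as described above will result in a success rate of only approximately 35" (per cent). The assumed rates for rESWT alone and for the combination are about 70% and 85%.
- How it was used: "On this basis we performed a Power analysis, both for a percentage of 35% as well as for various other percentages". The text then points to the results: "The results are summarized in Tables 7 and 8".
- Table 7 caption: "percentage of patients with treatment success of 40% when treated with C-E drugs alone (assuming n=50 patients per group").
- Table 8 caption: "percentage of patients with treatment success of 70% when treated with rESWT alone (assuming n=50 patients per group"). Table 8 therefore serves the comparison with rESWT alone, and Table 7 is the table for comparisons with C-E drugs.
- Table 9 caption (sample sizes for 80% power): "The percentage of patients with treatment success when treated with C-E drugs alone was set at 40" (per cent).
- The summary claims power above 0.8 for both comparisons with C-E drugs "when randomizing at least 49 patients into each group". The 49 is the continuity-corrected entry in the 70% row of Table 9.
- Section 5, Follow-up and statistical analysis, says that treatment success "will be tested with Fisher's exact test".

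**The concern.** The text announces an analysis at 35%, and the table that reports it is labelled 40%. Either the label or the figures must be wrong.

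Taken at face value, Tables 7 and 9 also disagree with each other. For 70% against 40%, Table 7 gives 92.4% continuity-corrected power with 50 per group, while Table 9 asks for 49 per group to reach only 80%. One extra patient per group cannot add 12 points of power.

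At stake is what a reader takes the power to be for rESWT alone against C-E drugs, one of the two comparisons the protocol says the study can test. If the true error lay in the figures, power would be well below what is printed.

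**Working it through.** **Inputs.** n = 50 per group, two-sided 5% (z = 1.960), control rate p0 = 0.35 (text) or 0.40 (caption), comparator rate p1 from the table rows. All are from Section 5.1.

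**Formula.** With d = |p1 − p0| and m = (p0 + p1)/2,

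power = Φ{ [d√n − 1.960·√(2m(1 − m))] / √(p0(1 − p0) + p1(1 − p1)) }.

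For the continuity-corrected column, n is replaced by n − 2/d.

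**Check of the formula on Table 8 (comparator 70%).** Computed for the 99.9, 90, 85 and 80% rows: 99.28/98.33, 71.15/61.22, 43.38/33.40, 20.88/14.17. Printed: 99.3/98.3, 71.2/61.2, 43.4/33.4, 20.9/14.2. All agree within 0.1 point, so this is the method that was used.

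**The key row of Table 7 (70%).**

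- At 35%: d = 0.35, m = 0.525. Numerator 0.35 × √50 − 1.960 × √0.49875 = 1.0907; denominator √(0.2275 + 0.21) = 0.6614; ratio 1.649; power 95.04%. Corrected n = 50 − 2/0.35 = 44.29; power 92.35%. Printed: 95.0/92.4.
- At 40%: d = 0.30, m = 0.55. Numerator 0.30 × √50 − 1.960 × √0.495 = 0.7424; denominator √(0.24 + 0.21) = 0.6708; ratio 1.107; power 86.58%. Corrected n = 50 − 2/0.30 = 43.33; power 81.28%.

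Difference between print and 40%: 95.0 − 86.6 = 8.4 and 92.4 − 81.3 = 11.1 points.

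**The other rows of Table 7 (normal / corrected).**

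| Row | Printed | At 35% | At 40% |
|---|---|---|---|
| 99.9% | 100/100 | 100/100 | 100/100 |
| 90% | 100/100 | 100/100 | 100/100 |
| 85% | 100/100 | 99.99/99.97 | 99.88/99.74 |
| 80% | 99.8/99.6 | 99.82/99.63 | 99.00/98.19 |
| 70% | 95.0/92.4 | 95.04/92.35 | 86.58/81.28 |
| 60% | 71.3/63.5 | 71.26/63.50 | 51.63/43.07 |
| 50% | 32.7/25.2 | 32.71/25.19 | 16.86/11.75 |
| 40% | 7.2/3.5 | 7.42/4.17 | no difference |

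The 70, 60 and 50% rows decide the matter: they match at 35% and miss by 8 to 20 points at 40%. The 40% row fits 35% only approximately. The value 1.1/0, which this formula does not reproduce, stands in the 35% row of Table 7 and in the 70% row of Table 8. In Table 8 that is the no-difference row, so by position 35% is the null of Table 7. Were the control rate 40%, the 40% row would be the null, yet it prints 7.2/3.5.

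**Table 9.** For 70% against control at 80% power, the three printed formulas (Kelsey / Fleiss / Fleiss with continuity correction) give, after rounding up:

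- at 40%: 43.2, 42.0 and 48.4, so 44/42/49, exactly as printed;
- at 35%: 32.0, 30.8 and 36.2, so 32/31/37.

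Seven of the eight rows match exactly at 40%. The 45% row computes to 1535/1534/1574 against 1502/1501/1540 printed. Table 9 was thus computed at its stated 40%.

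**Does the conclusion survive at 40%?** With 49 per group: 85.9% normal, 80.3% corrected. For the named test, taken as a pairwise two-sided Fisher test at unadjusted 0.05 (an assumption, since Section 5 fixes neither the pairs nor the level per pair), full enumeration for the 70% row with 50 per group gives 93.1% at 35% and 82.9% at 40%; with 49 per group at 40% it gives 81.5%.

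**The case against.** Four points can be made for the plan.

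1. The text says the analysis also covered other control rates from 10% to 99.9%, which literally includes 40%. That could license a 40% table, but it does not make figures computed at 35% right under a 40% label. The sentence also introduces Tables 7 and 8, not Table 9, and gives no reason for choosing 40%.
2. If only the caption is wrong, the printed powers are correct for the protocol's own hypothesis and nothing is overstated. This stands: the 8.4 and 11.1 points apply only to a reader who trusts the caption.
3. The 40% behind the minimum of 49 is not hidden, because Table 9 prints it. This also stands: what is missing is a reason and any remark that 40% is more conservative than the stated 35%.
4. Nothing in the design turns on it. The claim of power above 0.8 holds at both rates, and the combination arm has about 100% power against C-E drugs either way. That limits the weight of the point but does not remove the contradiction.

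**Conclusion.** The concern holds. Table 7's figures belong to a control rate of 35%, its caption says 40%, and Table 9 under the same 40% really uses 40%. Text, figures and the position of the null row all point to 35%; only the caption disagrees.

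The severity is minor. Under the caption, power for rESWT alone against C-E drugs is 86.6% (81.3% corrected), not 95.0% (92.4%). The more conservative rate in Table 9 raises the minimum from 37 to 49 per group. The planned 50 per group is enough for the protocol's claim at either rate, though at 40% and 49 per group the corrected power is only just above 80%.

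This rests on the protocol's assumed 70% for rESWT alone, an unadjusted two-sided 5% level and no allowance for dropout, as in the plan's own calculation.

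**What to change.** - Change the control rate in the Table 7 caption from 40% to 35% and keep the figures.
- At Table 9, and where the minimum of 49 per group is stated, say that these use 40%, a more conservative rate than the hypothesised 35%, and why.
- Add one sentence: if success on C-E drugs is 40%, power for rESWT alone against C-E drugs with 50 patients per group is about 81% (continuity-corrected) to 87% (normal approximation). The Fisher figure, about 83% for a pairwise two-sided test at unadjusted 0.05, may be added with that assumption stated.

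If 40% was intended throughout, the alternative is to keep the caption, recompute Table 7 at 40% and reconcile the 35% in the text.

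The cost is one number in a caption and two sentences, plus the disclosure of a less favourable power at 40%. Sample size, analysis and conduct are unchanged.

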6.1. Procedures in the event of Adverse Events

- Potential unwanted side effects of rESWT may be petechial bruises of the skin at the treatment side and temporary numbness. These unwanted side effects normally vanish within one or two days.
- Potential unwanted side effects of celecoxib and Eperisome are increasing the risk of cardiovascular events and gastrointestinal events, exhaustion, dizziness.
- Should any unwanted side effects persists for longer than usual, the investigators will treat these patients according to usual standard of care of the First Affiliated Hospital of Zhejiang University.

6.2. Procedures in the event of Emergency

The principal investigator is responsible for ensuring that procedures and expertise are available to cope with medical emergencies during the study.

6.3. Procedures in the event of Pregnancy

The subject must be instructed to inform the investigator if she becomes pregnant during the study. As pregnancy is a contraindication for treatment with rESWT, the patient will be

terminated from the study. The investigator will follow up the pregnancy until the outcome is known.

6.4. Patient data protection

Subjects' anonymity will be maintained. In order to guarantee confidentiality of records and documents that could identify subjects, subjects will only be identified by their assigned identification number on all case report forms (CRFs) and other records and documents. The investigator will keep a Patient Identification List with complete identification information (identification number, name, address, contact number) on each subject. Documents not for submission to the Medical Research and Ethics Committee of the First Affiliated Hospital of Zhejiang University and/or the Chinese Clinical Trial Register such as subject's written informed consent form will be maintained by the investigator in strict confidence.

6.5. Insurance

With respect to any liability directly or indirectly caused by the investigational products in connection with the proposed study, the principal investigator and the Department of Pain Medicine at the First Affiliated Hospital of Zhejiang University assumes liability by law for possible injury to the subject. The investigator and his/her staff will strictly follow the instructions of the manufacturer of the rESWT device Swiss DolorClast (Electro Medical Systems; Nyon, Switzerland) in accordance with the proposed protocol and any amendments thereto. Furthermore, the investigator and his/her staff will in general perform the proposed study in accordance with scientific practice and currently acceptable techniques and know how.

6.6. Rescue medication/procedure

rESWT itself does not require specific rescue medication / procedures.

7. Study Termination/Suspension

The principal investigator holds the right to suspend or terminate patient's participation in the proposed study in the event of deterioration of clinical condition at the discretion of the investigator.

7.1 Subject Withdrawal & Drop-out

Subjects are free to withdraw from the study at any time for any reason.

Subjects may also be withdrawn from the study at any time at the discretion of the investigator. Should a subject withdraw or is withdrawn, every effort will be made to complete and report the observations as thoroughly as possible. Possible reasons for withdrawal will be documented. For e.g.:

- adverse event(s)
- abnormal laboratory values
- improvement of subject's condition such that he/she no longer requires study treatment
- insufficient therapeutic effect
- protocol violation (eg. incorrectly enrolled or randomised)
- subject requires use of unacceptable concomitant medication
- subject not compliant with protocol procedures
- subject develops a condition during the study that violates the inclusion/exclusion criteria
- lost to follow-up
- death
- any other reason, in the investigator's opinion, that would impede the subject's participation in the study

7.2. Procedures for handling withdrawal

Subjects who withdraw or are withdrawn from the study will have the below information recorded:

- the reason(s) for their withdrawal,
- presence of any adverse events and if so will be followed up by regular scheduled visits, telephone contact and correspondence until satisfactory clinical resolution of adverse events is achieved,
- at least one follow-up contact (scheduled visit, telephone contact, correspondence) for safety evaluation during the 30 days following the last session of study treatment, and
- in the event of pregnancy, the subject should be monitored until conclusion of the pregnancy and the outcome of pregnancy reported.

7.3. Subject replacement policy

After randomization and the first rESWT plus C-E drugs, rESWT alone or C-E drugs alone treatment, no patient will be replaced.

7.4. Medications permitted or not permitted during the study.

No other adjunct pharmacological treatment for non-specific low back pain is allowed during the duration of the study. Other medications not permitted are as explained in the Exclusion Criteria. Medications permitted are those not mentioned in the Exclusion Criteria.

8. Ethical Consideration

The researchers have considered the ethical issues that may arise with the conduct of the proposed study. The proposed study will only be conducted after seeking approval from the Medical Research and Ethics Committee of the First Affiliated Hospital of Zhejiang University.

9. Subject Withdrawal & Compensation

Participation in the proposed study is completely voluntary. The participants will not be paid for joining the proposed study nor will they be expected to pay to join the proposed study. Participants are able to withdraw themselves from the proposed study at any time without any reason and consequences to their follow-up treatment. Standard routine care will still be provided to them. The researchers hold the right to use any data collected until a participant would withdraw from the proposed study.

10. Adverse Events

10.1. Definitions

Adverse event (AE)

Any untoward medical occurrence in a subject administered an investigational product and which does not necessarily have a causal relationship with treatment. An AE can therefore be any unfavourable and unintended sign, symptom, laboratory observation or disease temporally associated with the use of the investigational product, whether or not related to the investigational product.

The following should be reported as AE:

- treatment emergent symptoms which include:
 - medical conditions or signs or symptoms that were absent before starting study treatment, and

- medical conditions or signs or symptoms present before starting study treatment and worsen (increase severity or frequency) after starting study treatment;
- abnormal laboratory values or tests that induce clinical signs or symptoms or require therapy;
- any adverse experience even if no drug has been administered, for example during run in or wash out phase of the study; and
- any doubtful event should be treated as an AE.

Unexpected adverse event

Any adverse event not reported in the safety section of the Investigator's Brochure or if the event is of greater frequency, specificity or severity.

Serious adverse event (SAE)

Any adverse event occurring that:

- results in death, or
- is a life threatening adverse experience defined as any adverse event that places the subject, in the view of the investigator, at immediate risk of death from the reaction as it occurred. Note that this does not include a reaction that had it occurred in a more severe form, it would have caused death, and/or
- results in subject hospitalization or prolongation of existing hospitalization.

The following hospitalizations are not considered to be SAEs:

- those planned before entry into the study,
- elective treatment for a condition unrelated to study indication or study treatment,
- those that occur on an emergency outpatient basis and do not result in admission (unless fulfilling other criteria in SAE definition),
- parts of normal treatment or monitoring of the study indication and are not associated with any deterioration in condition,
- results in a significant or persistent disability or incapacity defined as any event that results in a substantial and/or permanent disruption of the subject's ability to carry out normal life functions,
- is a congenital anomaly or birth defect,
- is any instance of overdose, either accidental or intentional (suspected or confirmed), and/or

- is any other important medical event, based upon appropriate medical judgement, that may jeopardize the subject or may require medical or surgical intervention to prevent or avert one of the outcomes listed above.

